8.5 Adjudication Committee

An independent cardiovascular adjudication committee will be used to re-evaluate and confirm the investigator-reported diagnostic term of specific safety events (e.g. ischemic heart disease, heart failure, cardiomyopathy, or cardiac arrhythmias). Events will be reviewed blindly as they occur during the trial. Details regarding the adjudication process will be available in the relevant Adjudication Committee charter. The committee may provide expert reports at the end of the study.

The clinical database will be regularly searched by the clinical team for targeted adverse events including but potentially not limited to cardiac safety events. When an adverse event in these categories is identified, a follow-up form will be sent to the clinical site to document the adverse event in detail and to request the submission of any applicable supplemental data, which may be available, including copies of source documents. Source documents include, but are not limited to, relevant clinical notes, radiographs, ECGs, ultra-sonograms, operative and pathology reports, hospital discharge summaries. In addition, an interview with the patient conducted by the site (in person or via telephone) may be needed to fully clarify the circumstances of the event.

The outcome of the adjudication or the expert review will be captured in the clinical data base.

[figure not shown]
9 Data analysis

The primary analysis for this study will be conducted when all patients have completed the (double-blind) treatment epoch (Week 24 visit). All post-treatment follow-up data on efficacy endpoints (SPPB and gait speed) available at the time of the primary analysis will also be summarized to address the durability of functional benefits during the off-drug follow-up period. The final statistical analysis will be performed when all patients have completed Week 48 of the study.

All details regarding the statistical analysis will be documented in the statistical analysis plan which will be finalized prior to the data extraction for the primary analysis (Week 24) at interim database lock and the global study team group level unblinding.

9.1 Treatments

Study medication and concomitant medication will be analyzed with the safety analysis set.

9.1.1 Study medication

The number and percentage of patients who prematurely discontinued study medication will be summarized by reason for discontinuation.

Duration (days) of study medication administration will be summarized. For each patient, the number of days of drug exposure = last infusion date – first infusion date + 56 based on the infusion schedule for the study (intravenously every 4 weeks).

9.1.2 Concomitant medications

The number and percentage of patients using prior or concomitant medications will be summarized by Anatomical Therapeutic Classification (ATC) codes and treatment group, and grouped by anatomical main group (the 1st level of the ATC codes).

Prior medications are defined as drugs taken and stopped prior to first dose of investigational treatment. Any medication given at least once between the day of first dose of investigational treatment and the date of the last study visit will be a concomitant medication, including those which were started pre-baseline and continued into the treatment period. Prior or concomitant medication will be identified based on recorded or imputed start and end dates of medication taking. If it cannot be established that the use of a prior medication has ended prior to the first dose of investigational treatment due to a missing end date, then it will be considered concomitant.

9.2 Analysis sets

The Full Analysis Set (FAS) used for all efficacy analyses will consist of all randomized patients who received at least one dose of investigational treatment. Patients will be analyzed according to the treatment they were assigned to at randomization. Patients who entered the study before Amendment 2 will be pooled with fixed-dose patients as follow: bimagrumab 3 mg/kg patients will be analyzed as member of the 210 mg group, bimagrumab 10 mg/kg patients will be analyzed as member of the 700 mg dose group.

The safety (SAF) Analysis Set will consist of all patients who received at least one dose of study medication. Patients will be analyzed according to the treatment received. Patients who entered the study before Amendment 2 will be pooled with fixed-dose patients as detailed for the FAS.

Per-protocol (PP) Analysis Set will include all FAS patients who complete the study without major deviations from the protocol procedures. Major protocol deviations and the definition of the PP set will be identified and finalized based on blinded review of the data, prior to the data extraction for the primary analysis (EoT) and the global study team group level unblinding.

For patients who entered the study before Amendment 2 and have been treated for more than 6 months, data collected after the Week 24 visit will be listed.

9.3 Patient demographics and other baseline characteristics

All data for background and demographic variables will be listed by treatment and patient and summarized by treatment. Patient demographics will include age, sex, race, ethnicity, height,

weight and BMI. Other baseline disease characteristics include medical history, falls history, orthopedic history, perioperative assessment, blood transfusion history, tobacco history, cardiovascular risk factors, gait speed, LBM, [REDACTED] and SPPB.

Summary statistics will be presented for the patients in the FAS. Continuous variables will be presented with mean, median, 25th percentile, 75th percentile, standard deviation, minimum and maximum, and the number of non-missing observations.

Categorical data will be displayed via absolute and relative frequencies for each category (including a category labeled as ‘missing’ when appropriate).

9.4 Analysis of the primary variable

The primary analysis set for efficacy will be FAS.

9.4.1 Variable

The primary variable is change from baseline in Total LBM at Week 24.

9.4.2 Statistical model, hypothesis, and method of analysis

The aim of the study is to show that at least one bimagrumab treatment arm will increase Total LBM (change from baseline) compared with placebo at Week 24 by rejecting the null hypothesis described below at significance level $\alpha=0.05$ level (two-sided):

$$H_0: \mu_T = \mu_P \text{ vs. } H_1: \mu_T \neq \mu_P$$

where μ_T and μ_P are mean change from baseline of Total LBM at Week 24 for the bimagrumab dose group of interest (700mg or 210mg only) and placebo.

[figure not shown]
A mixed model will be used with change from baseline at all post-baseline visits (Week 12, and Week 24) as response variable, and treatment, visit, randomization strata as defined in [Section 5.3](#) and baseline LBM measurement as covariate. Two interaction terms (treatment*visit and baseline LBM*visit) will also be included in the model. An unstructured within subject correlation structure will be used for covariance matrix. The Kenward-Roger approximation will be used to estimate denominator degrees of freedom. REML (residual/restricted maximum likelihood) method will be used to estimate parameters.

The two-sided p-value for the least square mean (LSM) difference between the bimagrumab and the placebo groups at Week 24 (and at Week 12) will be reported for the difference. For the primary endpoint, the Holm-Bonferroni method will be used to adjust for type I error among the 2 comparisons at Week 24. No control for multiplicity will be made at Week 12. Total LBM data will be transformed with natural logarithm before this analysis.

9.4.3 Handling of missing values/censoring/discontinuations

The above analysis will be performed using all available data under the assumption that the probability of missing values of total LBM is independent of unobserved measurements (missing at random). Therefore the missing values will not be imputed for primary analysis.

The following sensitivity analysis will be performed to check the robustness of the primary analysis results.

- Fit the analysis model only to the completed cases (patients without missing LBM)
- Missing value imputation:

For this sensitivity analysis, we assume a “missing not at random” (MNAR) process meaning that missingness depends on the unobserved data. Suppose that patients in the bimagrumab arms who discontinue due to adverse events (AE), death (D) or unsatisfactory therapeutic effect (UTE) behave like placebo arm patients after study discontinuation. This assumption implies that the drug effect diminishes once bimagrumab arm patients discontinue from the study. To perform this analysis, a Bayesian multivariate normal imputation model using non-informative priors is fitted to the repeated total LBM measurements at baseline and Weeks 12, and 24 for all placebo patients. Based on this model, the conditional distribution of missing data given the observed data can be used to create multiple imputations for the missing values of patients in the bimagrumab arms who discontinue due to AE, D, UTE.

Missing data for all other subjects will be imputed under a MAR assumption, that is missing data are imputed based on the treatment-specific information for the repeated total LBM measurements at baseline and Weeks 12 and 24.

For each imputed and thus completed data set, the primary analysis model is then fitted as specified in [Section 9.4.2](#). The resulting sets of parameter estimates and associated covariance matrices are then combined to derive overall estimates, confidence intervals that adequately reflect missing data uncertainty as well as associated p-values using Rubin’s rules ([Little RJA and Rubin DB 2002](#)).

The results from all analyses will be discussed with reference to the plausibility of their respective underlying assumptions.

9.4.4 Supportive analyses

As supportive analysis, the primary analyses will be repeated using the PP analysis set.

In addition, dose response modeling will be performed using the MCP-Mod approach, which considers the following models:

1. Three parameter Emax: $f(d) = E_0 + E_{max}d / (ED_{50} + d)$
2. Sigmoidal Emax with $h=2$: $f(d) = E_0 + E_{max}d^h / (ED_{50}^h + d^h)$
3. Exponential: $f(d) = E_0 + E_1 \exp(d/\delta) - 1$
4. Linear: $f(d) = E_0 + \beta * d$

Where d is the dose level, ED_{50} the dose that gives 50 percent of the maximum effect, h the hill coefficient; δ and β the rate of change for the exponential and linear models respectively, E_0 the basal effect at $d=0$ and E_1 the scale parameter in the exponential model.

In the MCP-Mod approach, all statistically significant models listed above will be averaged in order to estimate the median dose for a given targeted response via inverse prediction along with corresponding 95% intervals using a bootstrap re-sampling method.

Since the design of this study is limited to having only 3 active doses, another dose response sigmoidal Emax model will also be considered which allows for estimation of the Hill coefficient (h). In this model, the fixed dose of 70 mg, 210 mg, and 700 mg from each patient will be normalized by their baseline weight in kg (i.e., the fixed dose will be divided the

baseline weight) to form a mg/kg dose regressor. The specific model to be applied to the mg/kg regressor will be the non-standardized sigmoidal Emax model. The mean dose response and corresponding asymptotic 95% confidence intervals (i.e., fiducial intervals) will be provided using the inverse prediction approach again.

The non-standardized sigmoidal Emax model is parameterized as follows:

$$f(d) = E_0 + E_{max}d^h / (ED_{50}^h + d^h)$$

In choosing which dose response model to select for estimating dose as well as characterizing the entire response profile, the MCP-Mod approach is the default under the rule of parsimony, provided it fits the data well and results in intervals for estimating dose that are smaller than the 4 parameter Emax model.

To evaluate the homogeneity of the estimates within subgroups, forest plots displaying treatment group differences (or ratios) and corresponding 95% confidence intervals by subgroup, together with the relative position of the overall treatment effect, will be produced. In the statistical models, a treatment by subgroup interaction term will be added to allow for the analysis of the treatment effect within a subgroup. Subgroup analyses will include for example analyses of patients enrolled under original protocol versus those enrolled under protocol amendment 2.

9.5 Analysis of secondary [REDACTED] variables

9.5.1 Efficacy variables

9.5.1.1 Gait speed and Short Physical Performance Battery (SPPB)

The change from baseline at Week 24 and Week 48 in gait speed and in SPPB will be analyzed similar to the primary variable. A log transformation may be used if warranted. An unstructured within subject correlation structure will be used for the covariance matrix.

In addition, dose response modeling will be performed for both gait speed and SPPB using the MCP-Mod approach.

The following testing strategy will be used to control for multiplicity of endpoints and doses to be tested: if both doses (210 and 700 mg) are statistically significantly different from placebo at $\alpha=0.05$ two-sided for the primary endpoint, then a fixed sequence approach will be applied for both Gait Speed and Short Physical Performance Battery (SPPB) at week 24 using the same linear mixed model for repeated measures and $\alpha=0.05$ two-sided at each stage. The first inference will compare the 700 mg group to placebo for Gait Speed, followed by a second inference comparing the 210 mg group to placebo for Gait Speed. The third inference will compare the 700 mg group to placebo for SPPB, followed by a fourth inference comparing the 210 mg group to placebo for SPPB. Additionally, the fifth inference will compare the combined 700 mg and 210 mg group to placebo for the incidence of fall observed till the time of the interim analysis. The analysis conducted at Week 24 for falls will include available incidence of falls also collected from patients with visits beyond Week 24. The analysis of the fall data will be performed based on the assumption that the differences in incidences of fall within the active bimagrumab doses (700 mg and 210 mg) is small compare to the differences of those doses to the placebo arm.

The sequence of the endpoints has been decided based on the anticipated probability of showing statistical significance of bimagrumab over placebo, the clinical importance is not considered for this sequence determination, as each endpoint is clinically important.

9.5.1.3 Falls

The frequency of having at least one fall up to Weeks 24 and 48 will be summarized by treatment group. The time to the first fall may also be assessed using a plot of the Kaplan-Meier product limit estimates and a log rank test provided there are a sufficient number of events. Negative binomial regression may also be used to analyze fall event rates. All details regarding the analyses of falls will be documented in the statistical analysis plan. The numbers of patients meeting the criteria for the responder endpoint derived from SPPB, Gait Speed and incidence of falls by Week 24 and 48 will be summarized by treatment group. A logistic regression may be used to determine the treatment effect.

9.5.2 Safety variables

All safety evaluations will be performed on the safety set (SAF). Some safety analyses might be repeated on the subset of patients randomized after Amendment 2 that is patients who received a fixed dose of investigational treatment.

9.5.2.1 Cardiac Safety Analysis

The frequency of experiencing at least one cardiac event of special interest (AESI) – cardiomyopathy, ischemic heart disease, heart failure, or cardiac rhythm disturbances (brady/tachyarrhythmias) - will be summarized by treatment group. In addition, the relative risk (to placebo) of experiencing at least one AESI (based on the confirmed events) will be calculated with 95% confidence intervals for each of the bimagrumab treated groups versus placebo. The results of these analyses will be presented in tabular form. If a substantial number of events occur, data may also be summarized graphically using adverse events dot plots (incidences and relative risks) per experimental dose.

Depending on the rarity of the events, a Kaplan-Meier plot for time-to-the first event with a censored adjusted median time and corresponding 95% confidence intervals may be presented for each treatment group. Differences between placebo and each of the bimagrumab treated groups will be further assessed by a log-rank test if the Kaplan-Meier plots provide a clinically warranted rationale.

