In addition, provided again that there are a sufficient number of events ($\geq 10\%$ of patients have at least one event), the time to the first cardiac event over the course of the study (as calculated relative to the start of first infusion of study drug) will be estimated for each treatment group and “Active Total: Safety”. Kaplan-Meier estimates for median time to first cardiac event with 95% confidence interval, 25th and 75th percentiles will be presented. Patients not experiencing a cardiac event will be censored at the time of study completion, premature discontinuation or if ongoing in the study at the last available assessment date. The survival distributions of time to first cardiac event will be compared between each active bimagrumab treatment group, “Active Total: Safety” and placebo by means of the log-rank statistic (see [Section 3.11](#) [Statistical methodology and assumptions]).

As the number of cardiac rhythm disturbance, heart failure, ischemic heart disease and cardiomyopathy events are expected to be low, descriptive statistics (see [Section 3.2](#) [Precision and summary statistics]), will be performed on the questions listed in the Cardiac rhythm disturbances, Heart failure, Ischemic heart disease and Cardiomyopathy eCRFs. Any information recorded in the Adverse events eCRF for an AE which is deemed to have an AE classification of “Cardiac rhythm disturbances”, “Heart failure”, “Ischemic heart failure” or “Cardiomyopathy” will also be summarized descriptively, if relevant.

Orthopedic events

Orthopedic events (i.e. fracture healing complications) will be summarized in a similar manner as the cardiac safety events described above. These events are expected to be rare and orthopedic information is recorded in the Orthopedic complications eCRF.

Hospitalizations

Hospitalizations will be summarized in a similar manner as the orthopedic/cardiac safety events described above. Descriptive statistics (see [Section 3.2](#) [Precision and summary statistics]) will be presented for certain characteristics as recorded in the Hospitalization eCRF. These are:

- Number of patients hospitalized and number of hospitalization events (E).

- Reasons for hospitalization:
 - Injurious fall with fracture.
 - Other.
- Place of discharge:
 - Home.
 - Long-term care facility.
- Average duration of hospitalizations (days) = Duration of hospitalization (Date of discharge – date of admission) / Number of hospitalizations.

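### From the SAP's 10% gate up to about 40% incidence, the Kaplan-Meier median for first cardiac or orthopedic event is rarely estimable; add cumulative incidence at fixed days

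*Protocol*

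**What the plan says.** Protocol 9.5.2.1 treats the time-to-event display as optional and lets it depend on how rare the events turn out to be. In that case, "a Kaplan-Meier plot for time-to-the first event with a censored adjusted median time and corresponding 95% confidence intervals may be presented".

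SAP 2.11.6 (Cardiac safety events) is firmer. The analysis of time to first cardiac event runs if at least 10% "of patients have at least one event". It then commits to these numbers: "Kaplan-Meier estimates for median time to first cardiac event with 95% confidence interval, 25th and 75th percentiles will be presented". They are given for each treatment group and for the pooled active groups, with a log-rank comparison against placebo. Patients without an event are censored at study completion, at premature discontinuation, or at the last assessment if still ongoing.

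Orthopedic events "will be summarized in a similar manner as the cardiac safety events described above", and SAP 3.11.4 applies the same LIFETEST and log-rank method to the first orthopedic event. The SAP calls orthopedic events rare. Of the cardiac categories it says "As the number of cardiac rhythm disturbance, heart failure, ischemic heart disease and cardiomyopathy events are expected to be low", as its reason for summarising the individual cardiac eCRF questions descriptively. Neither document gives an expected rate for the composite of at least one cardiac event, or for orthopedic events.

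**The concern.** The gate and the statistic do not match. The gate opens at 10% of patients with an event, but the headline statistic exists only when the Kaplan-Meier curve falls to 50%. The upper quartile needs it to fall to 25%, and the lower quartile to 75%. For most incidences that pass the gate, the median cell would read as not estimable.

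Follow-up will also be unequal. Patients who stop treatment have an end-of-treatment visit about 28 days after the last dose and an end-of-study visit 4 weeks later (protocol 5.5.9 and the footnote to Table 6-1). Only about 120 of 245 patients are expected to complete 48 weeks, and some will still be in follow-up at the primary analysis. Kaplan-Meier is the natural way to state absolute risk by arm under such censoring. As specified, it would usually give a curve and a p-value, with no risk figure and interval to quote.

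**Working it through.** The documents contain no event rate, event count or power figure for these endpoints, so there is no planned number to reproduce. The check is whether the named statistics can be estimated.

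**Inputs from the documents**
- Arm sizes: 70, 70 and 70, plus 35 in the 70 mg arm (protocol 9.7).
- Gate: at least 10% of patients with an event (SAP 2.11.6). It is not stated whether this applies per arm or overall.
- Retention: 245 randomised, about 200 to Week 24, about 120 to Week 48 (protocol section 4). That is 45/245 = 18% lost before Week 24, 80/245 = 33% lost between Weeks 24 and 48, and 120/245 = 49% followed to Week 48.

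**Assumptions**
- True 48-week incidence, varied from 10% to 50%.
- Exponential event times.
- Timing of losses within each half of the study.

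**Step 1: events needed with full follow-up**
- Median: n × 0.50 = 35 of 70 (18 of 35).
- Gate, if per arm: n × 0.10 = 7 of 70 (4 of 35).

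**Step 2: exact binomial probability, full follow-up**

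P(X ≥ 35), X ~ Bin(70, p): 3 × 10⁻¹⁷ at p = 10%, 2 × 10⁻⁸ at 20%, 0.04% at 30%, 5.7% at 40%.

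P(X ≥ 18), X ~ Bin(35, p): 8 × 10⁻¹⁰, 3 × 10⁻⁵, 0.6% and 11% at the same risks.

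**Step 3: simulation with the protocol's attrition, n = 70, 3,000 arms per row**

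| True 48-week incidence | Gate opens (per arm) | Lower quartile reached | Median reached | Upper quartile reached |
|---|---|---|---|---|
| 10% | 32.9% | 0.2% | 0.0% | 0.0% |
| 15% | 76.6% | 3.5% | 0.0% | 0.0% |
| 20% | 95.1% | 17.8% | 0.0% | 0.0% |
| 25% | 99.1% | 49.1% | 0.0% | 0.0% |
| 30% | 99.9% | 78.2% | 0.2% | 0.0% |
| 40% | 100.0% | 99.1% | 7.3% | 0.0% |
| 50% | 100.0% | 100.0% | 50.9% | 0.0% |

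A separate simulation of 4,000 arms per scenario, with losses spread uniformly within each half of the study, agrees. The median was reached in 0.0% of arms at 10%, 15% and 20%, 0.1% at 30% and 8% at 40%.

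**Step 4: other settings**
- 70 mg arm (n = 35), same attrition: median reached in 0.0% at 10–15%, 0.1% at 20%, 1.9% at 30%, 15.0% at 40%.
- Pooled active groups (70 + 70 + 35 = 175), same attrition: 0.0% up to 30%, 1.2% at 40%.
- Primary-analysis cut with censoring spread over Weeks 24–48, n = 70: 0.4% at 10%, 1.0% at 20%, 3.2% at 30%, 13.1% at 40%. At the lower risks these are mostly tail effects with few patients at risk. The upper quartile is reached in under 1% up to 40%.

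**Step 5: what a fixed-time risk would give**

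At the gate, with full follow-up, 7/70 = 10% has a Wilson 95% CI of about 4.9% to 19.2%. At 15% the half-width is 1.96 × √(0.15 × 0.85 / 70) = 8.4 points. For a difference between two arms of 70 at 15% it is 1.96 × √(2 × 0.15 × 0.85 / 70) = 11.8 points. Attrition widens these somewhat, but the estimates can be reported where the median cannot.

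**The case against.** The strongest reply is that little is lost, and most of it stands.

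- **Other summaries are planned.** Protocol 9.5.2.1 has the relative risk of at least one cardiac event against placebo with a 95% CI. Protocol 9.5.2.2 has odds ratios and/or absolute risk differences with CIs for orthopedic complications. SAP 2.11.6 and 3.11.8 add odds ratios with CIs. SAP 2.11.6 gives exposure-adjusted rates for treatment-emergent events of special interest, including cardiac and fracture-healing categories. The SAP's general adverse-event section tabulates events by interval, using patients still in the study as denominator. The curve and log-rank test need no median. A reader might infer that only crude proportions are left; the documents do not support that. The exposure-adjusted rates, however, are treatment-emergent and based on MedDRA queries, and none of these summaries gives the risk of a first event by a fixed day over the whole study.
- **The commitment is conditional.** A reader might infer that an empty median is bound to be reported. The protocol wording is optional, and below the SAP's gate nothing is run. If events are as infrequent as the SAP expects, the problem may never arise.
- **The statistics are not always blank.** The gate has no upper limit, and the lower quartile is often reached near 30% incidence. Deleting the quartiles would therefore discard usable results.
- **The code is nearly there.** The LIFETEST call in SAP 3.11.4 already writes out survival estimates; what is missing is a table line.
- **Orthopedic events rest on the SAP alone.** Protocol 9.5.2.2 plans no Kaplan-Meier analysis for them. SAP 2.11.6 and 3.11.4 do so explicitly.

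**Conclusion.** The point holds as a minor reporting weakness. Once the SAP's gate opens, the only Kaplan-Meier numbers it names are the median and quartiles. With 70 patients per arm and the protocol's own attrition, the median is essentially never estimable up to 30% incidence and is reached in 7–8% of arms at 40%. The upper quartile is not reached, and the lower quartile is available from about 25–30%. The loss is confined to a censoring-aware absolute risk by arm for first cardiac or orthopedic event over the study.

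The conclusion rests on assumed incidences, exponential event times and assumed loss timing, because the documents state none of these. The range and the alternative censoring patterns do not change it materially. The gate counts in Step 1 assume the 10% applies per arm.

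It does not follow that cardiac and orthopedic harm goes unanalysed, that any estimate is biased, or that the primary endpoint is touched. Nor need hospitalizations be included: the SAP lists descriptive items for them, and 3.11.4 names only falls, cardiac and orthopedic events.

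**What to change.** In SAP 2.11.6 (cardiac and orthopedic events) and 3.11.4:
- Report the Kaplan-Meier cumulative incidence with 95% CI at Day 168 and Day 336 for each arm, and the difference from placebo at those days with its 95% CI.
- Show the number still at risk at each day, since few patients will have reached Day 336 at the primary analysis.
- Keep the curve and the log-rank test, and show the median and quartiles only where they are reached.
- State whether the 10% gate applies per arm or overall.
- Check that the tabulated estimates are by treatment arm and not within the covariate strata named in the example code.

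Align the optional wording in protocol 9.5.2.1 at the next opportunity.

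The cost is a few lines of SAP text and one added table block. It needs no new data, visits or model, and nothing usable is lost.
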